#### **4.3.2 Exclusion criteria**

**Subjects are not permitted to enroll in the study if any of the following criteria are met:**

1. Subject is receiving any investigational drugs or using any experimental devices in addition to LCM.
3. Subject  $\geq 6$  years of age has a lifetime history of suicide attempt (including an actual attempt, interrupted attempt, or aborted attempt), or has suicidal ideation in the past 6 months as indicated by a positive response (“Yes”) to either Question 4 or Question 5 of the Columbia-Suicide Severity Rating Scale (C-SSRS) at Screening.

**Subjects who have participated in SP847 or other LCM pediatric clinical studies in epilepsy are not permitted to enroll in the study if any of the following criteria are met:**

2. Subject meets either of the following:
  - a. Withdrawal criteria for the primary study (with the exception of subjects who discontinued due to a dose reduction or status epilepticus). For subjects entering from EP0060, if the subject (or legal guardian) withdraws consent solely due to route of LCM administration (iv) or if the subject requires more than 10 iv LCM infusions, the subject may be allowed to participant in SP848 after discussion with and agreement from the Medical Monitor.
  - b. Ongoing serious AE (SAE).

**Subjects who enroll directly into SP848 without previous participation in a LCM clinical study are not permitted to enroll in the study if any of the following criteria are met:**

4. Subject has ever received LCM.
5. Subject has any medical or psychiatric condition that, in the opinion of the investigator, could jeopardize or would compromise the subject's ability to participate in this study.
6. Subject has a medical condition that could reasonably be expected to interfere with drug absorption, distribution, metabolism, or excretion.
7. Subject has a known hypersensitivity to any component of the investigational medicinal product.
8. Subject is a female of childbearing potential and does not practice an acceptable method of contraception for the duration of the study.
  - Medically acceptable contraceptive method includes oral or depot contraceptive treatment with at least 30 $\mu$ g ethinylestradiol per intake (or 50 $\mu$ g if associated with carbamazepine [or other strong enzyme inducers, eg, phenobarbital, primidone, oxcarbazepine]) which must be used in conjunction with a barrier method. Sexual abstinence is also an acceptable method of contraception.

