#### **4.3.3 Criteria for withdrawal**

All subjects discontinuing treatment with study medication for any reason should taper off medication as described in Section 4.4.1. Whenever possible, these cases should be discussed with the medical monitor prior to withdrawing the subject from the study. All subjects who withdraw from the study due to an AE must be followed until resolution of the event or until the event is considered stable. The following criteria for subject withdrawal from SP848 are outlined below. Additional discontinuation criteria for potential drug-induced liver injury (PDILI) are presented in Section 4.3.3.1.

Participation in this study **must** be discontinued for any of the following reasons:

1. Intolerable AEs, including clinically relevant abnormal laboratory findings that, in the opinion of the investigator, preclude further participation in the study
2. The request of the Sponsor or a Regulatory Agency

3. Subject achieves menarche during the study and does not practice an acceptable method of contraception for the duration of the study (unless sexually abstinent).
4. Subject becomes pregnant, as evidenced by a positive pregnancy test.
5. Subject has a corrected QT interval (QTc) of greater than or equal to 500ms as confirmed by a cardiologist overread on any ECG.
6. Subject develops a second-degree atrioventricular (AV) block while awake or develops a third-degree AV block at any time.
7. Subject is unwilling or unable to continue, or the caregiver/parent/legal guardian is unwilling or unable to allow the subject to continue in the study.
8. Investigator's decision that withdrawal from further participation would be in the subject's best interest.
9. Subject experiences convulsive status epilepticus (if none had occurred prior to study entry) and is compliant with study treatment
11. For subject who did not complete a C-SSRS at Screening, subject has a lifetime history (prior to study entry or since study start) of suicide attempt (including an actual attempt, interrupted attempt, or aborted attempt) of the screening version of the C-SSRS. The investigator must withdraw the subject from the study and immediately refer the subject to a Mental Healthcare Professional.

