12. For all subjects  $\geq 6$  years of age, regardless of whether or not a C-SSRS was completed at Screening, subject has actual suicidal ideation as indicated by a positive response ("Yes") to either Question 4 or Question 5 of the "since last visit" version of the C-SSRS. The subject should be referred immediately to a Mental Healthcare Professional and must be withdrawn from the study.

Participation in this study **may** be discontinued for any of the following reasons:

1. Any clinically relevant change in medical or psychiatric condition (if in the opinion of the investigator, the condition warrants discontinuation from the study).
2. Subject requires a medication that is not permitted by the protocol.
3. Subject and/or delegated caregiver is unable to manage the completion of the diary or is noncompliant with study procedures or medication, in the opinion of the investigator.
5. For subject who did not complete a C-SSRS at Screening, subject had actual suicidal ideation in the past 6 months as indicated by a positive response ("Yes") to either Question 4 or Question 5 of the screening version of the C-SSRS. The investigator must immediately refer the subject to a Mental Healthcare Professional and use clinical judgment as to whether to withdraw the patient from the study.

If a subject from SP848 enrolls in EP0060 and either withdraws consent solely due to route of LCM administration (iv) or if the subject requires more than 10 iv LCM infusions, the subject may be allowed to return to SP848 after discussion with and agreement from the Medical Monitor. If a subject from SP848 is advised to withdraw from the SP848 after participation in EP0060, the subject will be required to return to the SP848 to complete the required ETV and Safety Follow-up assessments.

Investigators should attempt to obtain information on subjects in the case of withdrawal. For subjects considered as lost to follow up, the investigator should make efforts (at least 1 phone call and 1 written message to the subject), and document his/her efforts (date and summary of the phone call and copy of the written message in the source documents), to complete the final evaluation. All results of these evaluations and observations, together with a narrative description of the reason(s) for removing the subject, must be recorded in the source documents. The eCRF must document the primary reason for withdrawal.

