## 5.1 Screening Visit

Beginning with Protocol Amendment 4, at selected sites, up to approximately 100 eligible pediatric subjects  $\geq 4$  years to  $\leq 17$  years of age who have not previously participated in a LCM clinical study will be permitted to enroll directly into SP848.

At the Screening Visit, subjects entering directly into SP848 (ie, subjects who have not participated in SP847 or another applicable LCM pediatric clinical study in epilepsy) will be evaluated for their suitability for enrollment in SP848. The Screening Visit is not applicable for subjects who have participated in SP847 or another applicable LCM pediatric clinical study in epilepsy; the first visit in SP848 for these subjects is Visit 1 (see Section 5.3).

The Screening assessments will be conducted up to 14 days prior to the first administration of LCM. It is acceptable for the Screening assessments to be conducted on more than 1 day, although it should not be done over longer than 1 week. Prior to the conduct of any study-related procedures, a complete explanation (both verbally and written) of the nature and purpose of the study will be given to the subject (when possible or as required according to local IRBs/IECs) and the subject's parent/legal guardian by the investigator (or designee). The subject's parent/legal guardian will be requested to sign and date the IRB/IEC-approved Informed Consent Form. When possible, or as required by the local IRB/IEC, the subject will be requested to give assent to participate in the study. Each subject's eligibility for the study will be determined on the basis of the inclusion/exclusion criteria and the results of the following pretreatment assessments (for further details of the assessments and the required procedures and methods, please refer to Section 6, Section 7, and Section 8 of this protocol).

- Concomitant medications assessment
- Concomitant AEDs assessment
- Medical history assessment
- Seizure history over the past 4 weeks (historical Baseline)
- Complete physical examination
- Complete neurological examination
- 12-lead ECG (2 interpretable recordings approximately 20 to 30 minutes apart prior to vital signs assessment and collection of blood sample)
- Vital signs assessment (blood pressure and pulse)
- Body weight assessment
- Height assessment
- Blood sample for clinical chemistry, hematology, and endocrinology
- Urine sample for urinalysis
- Serum pregnancy test for female subjects of childbearing potential

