## **5.2 Titration Visit(s) (TV1, TV2, TV3, TV4, TV5, TV6)**

Eligible subjects who enter directly into SP848 (without prior participation in SP847 or another applicable LCM primary study) will initiate treatment with LCM at TV1, and the LCM dose will be titrated over the following week(s). Titration Visits are not applicable for subjects who have participated in SP847 or another LCM primary study; the first visit in SP848 for these subjects is Visit 1 (see Section 5.3).

At TV1, subjects who have enrolled directly into SP848 will receive a single dose of LCM (1mg/kg [oral solution] or 50mg [tablet]) during the clinic visit. Over the following days, subjects will be administered LCM 1mg/kg bid (oral solution) or LCM 50mg bid (tablet), and will begin titrating in weekly increments of 2mg/kg/day (oral solution) or 100mg/day (tablet) up to a level to optimize tolerability and seizure control (not to exceed 12mg/kg/day [or 600mg/day based on body weight, whichever is lower]). Subjects must be on each LCM dose for at least 5 days before titrating up to the next dose. It should be noted, in cases of incomplete doses (eg, subject spits out all or a portion of the syrup), missed doses, or administration of an erroneous volume of syrup, study medication should not be readministered and these cases would not be considered dose reductions. The LCM dose titration steps are summarized in Section 4.4.1.2.

A total of up to 6 Titration Visits may be required (eg, for a subject whose dose is titrated to the maximum permitted dose of LCM 12mg/kg/day). However, based on tolerability and seizure control, a subject's LCM dose may be titrated to a lower dose level; in such a case, fewer than 6 Titration Visits would be required.

The following assessments are required for each TV:

- Concomitant medications assessment
- Concomitant AEDs assessment
- Brief physical examination
- Brief neurological examination
- 12-lead ECG (2 interpretable recordings approximately 20 to 30 minutes apart prior to vital signs assessment and collection of any blood samples)

- Vital signs assessment (blood pressure and pulse)
- Body weight
- Blood sample for clinical chemistry, hematology, and endocrinology (TV4 only)
- Urine sample for urinalysis (TV4 only)
- LCM return/compliance (as applicable)
- Subject diary assessment
- C-SSRS
- Adverse event reporting
- Health care resource use
- Dispense subject diary
- Dispense LCM (as applicable)

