### 5.3 Visit 1 (Week 0)

For subjects who completed SP847, Visit 1 for SP848 was the same as Day 2 of the second PK collection time period (which may include an overnight stay at a hospital or medical facility) in SP847 (Day 28 for Cohorts 1, 2, 3, and 5 with maximum recommended dose of 8mg/kg/day; Day 35 for Cohorts 2 to 5 with maximum recommended dose of 10mg/kg/day; and Day 42 for Cohorts 2 to 5 with maximum recommended dose of 12mg/kg/day). For subjects who discontinued SP847 due to a dose reduction or status epilepticus, Visit 1 was the Early Termination Visit in SP847. For subjects in SP847 who were titrated up to the maximum permitted dose of 600mg/day sooner than the study schedule would ordinarily indicate (based on body weight) and who enroll in SP848, the Early Termination Visit of SP847 also served as Visit 1 for SP848.

For subjects who enroll in SP848 after participation in other LCM pediatric clinical studies besides SP847 (ie, SP0966 and EP0060) in epilepsy, SP848 Visit 1 will be specified in the respective primary study protocol.

For subjects who enter directly into SP848 (without prior participation in SP847 or other LCM pediatric clinic studies in epilepsy), the LCM dose will be titrated at weekly intervals as described in Section 4.4.1.2 and Section 5.2. These subjects will reach Visit 1 either (1) when the LCM dose is titrated to a level that, in the opinion of the investigator, optimizes tolerability and seizure control, or (2) when the maximum permitted LCM dose is reached (12mg/kg/day [or 600mg/day based on body weight, whichever is lower]). In the case of a subject who requires a dose reduction during the Titration Visits, the subject's LCM dose will be returned to the

previous dose level and the next clinic visit will be Visit 1 at the reduced level. Visit 1 should occur at least 5 days after the final TV. At Visit 1, the progress in SP848 for subjects who entered directly into SP848 and for subjects who have enrolled from SP847 or other LCM pediatric clinical studies in epilepsy will be aligned; subsequent regularly scheduled clinic visits for all subjects will be at 4-week intervals as outlined in the following sections.

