#### **8.4.6 Assessment of suicidality**

Suicidality will be assessed by trained study personnel using the C-SSRS (Columbia University Medical Center, 2008). For subjects  $\geq 6$  years of age, this scale will be used for screening as well as to assess suicidal ideation and behavior that may occur during the study. The C-SSRS will be completed according to the tabular schedule of study procedures, [Section 16.1](#).

Subjects enrolling directly who are  $\geq 6$  years of age will complete the "Baseline/Screening" version of the C-SSRS at Visit 1 and will complete the "Since Last Visit" version at subsequent

visits. If a subject becomes 6 years of age during the study, the “Already Enrolled” version of the C-SSRS should be used at the first visit at which the subject is 6 years of age and the “Since Last Visit” version used at subsequent visits.

The C-SSRS is not validated and will not be used for subjects <6 years of age. Subjects should be monitored for any changes in mood, ideas, or behavior for warning signs of depression. The investigator should be aware of common warning signs that might be a signal for risk of depression. For common signs and symptoms of depression in children younger than 6 years old, reference should be made to the current version of the Diagnostic and Statistical Manual of Mental Disorders. Parents and caregivers should also be advised accordingly and effort should be made at clinic visits to specifically assess potential depression.

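### For directly enrolled children aged 6 or older, Section 8.4.6 assigns the baseline C-SSRS form to Visit 1, when they are already on lacosamide, so a Question 4 or 5 Yes there meets no C-SSRS withdrawal criterion

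*Protocol*

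**What the plan says.** Section 8.4.6 states that directly enrolled subjects aged 6 or older "will complete the 'Baseline/Screening' version of the C-SSRS at Visit 1", with the Since Last Visit version at later visits. It names no version for the Screening Visit or for Titration Visits (TV) 1 to 6.

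Other sections set the timeline for the same subjects:

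- **Screening.** Exclusion criterion 3 in Section 4.3.2 depends on a positive answer to Question 4 or "Question 5 of the Columbia-Suicide Severity Rating Scale (C-SSRS) at Screening". Section 5.1 includes the C-SSRS among the items when it bases eligibility on the "results of the following pretreatment assessments".
- **Dosing.** Section 5.2 says these subjects "will initiate treatment with LCM at TV1" and lists a C-SSRS at each TV.
- **Visit 1.** Section 5.3 says "Visit 1 should occur at least 5 days after the final TV". Table 16-1, footnote h, confirms that direct enrollers have the C-SSRS at Visit 1.

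Section 4.3.3 contains three C-SSRS withdrawal criteria:

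- **Mandatory criterion 11** (suicide attempt): "For subject who did not complete a C-SSRS at Screening, subject has a lifetime history".
- **Mandatory criterion 12** (Question 4 or 5 ideation, all subjects aged 6 or older). It is tied to the since-last-visit "version of the C-SSRS. The subject should be referred immediately to a Mental Healthcare Professional and must be withdrawn from the study".
- **Optional criterion 5** (ideation on the screening version): "For subject who did not complete a C-SSRS at Screening, subject had actual suicidal ideation in the past 6 months".

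**The concern.** Visit 1 is the first SP848 visit for subjects rolling over from another lacosamide study, and the wording of 8.4.6 would suit them. It does not suit direct enrollers, who have by then been screened, dosed and titrated.

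Two things follow. First, the form prescribed for an on-treatment visit is not the form that triggers the mandatory rule. Criterion 12 is meant to remove discretion: immediate referral to a mental health professional and withdrawal. At Visit 1 the version label turns this into investigator judgement, and the written referral instruction, found only in criteria 11, 12 and optional 5, is not invoked. Second, the screening version, as the exclusion criterion and optional criterion 5 use it, looks back 6 months for ideation. At Visit 1 that period mixes time before and after the first dose, so the form cannot by itself separate emergent ideation from history.

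**Working it through.** No sample size, power or error rate is involved. The check is a timeline, a reading of the criteria and a head count.

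**1. Time on lacosamide at Visit 1.** Inputs from Sections 5.2 and 5.3: first dose at TV1 (day 0); 1 to 6 TVs; weekly steps, with at least 5 days on each dose; Visit 1 at least 5 days after the last TV.

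Days on drug at Visit 1 = (number of TVs − 1) × spacing + gap from last TV to Visit 1.

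- Shortest: (1 − 1) × 7 + 5 = 5 days.
- Six TVs at 5-day spacing and a 5-day gap: 5 × 5 + 5 = 30 days.
- Six TVs at weekly spacing and a 5-day gap: 5 × 7 + 5 = 40 days.
- Six TVs at weekly spacing and a 7-day gap: 5 × 7 + 7 = 42 days.

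Visit 1 therefore falls about 5 to 42 days after the first dose. The protocol sets no maximum; 42 assumes weekly steps without delay.

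**2. First visit that 8.4.6 assigns to the Since Last Visit version.** This is Visit 2 (Week 4): 5 + 28 = 33 to 42 + 28 = 70 days after the first dose, or 33 − 7 = 26 to 70 + 7 = 77 days with the 7-day visit window. This range holds on 8.4.6 alone, without the table footnotes.

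**3. Criteria met by a Question 4 or 5 Yes at Visit 1, age 6 or older.**

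| C-SSRS done at Screening? | Version used at Visit 1 | Mandatory 12 | Optional 5 |
|---|---|---|---|
| Yes (as 5.1 requires) | Baseline/Screening (as 8.4.6 prescribes) | not met | not met |
| Yes | Since Last Visit | met | not met |
| No | Baseline/Screening | not met | met |
| No | Since Last Visit | met | not met |

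Mandatory criterion 11 concerns attempts rather than Questions 4 and 5, and it also requires that no Screening C-SSRS was done. The first row is the fully compliant path, and no C-SSRS criterion applies there.

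**4. Table footnotes.** Footnote c of Table 16-3 and footnote p of Table 16-1 do mention the since-last-visit version. Both are written for subjects already enrolled, who first complete an already-enrolled form and switch afterwards. Neither clearly fits a newly screened child, and neither agrees with 8.4.6.

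**5. How many subjects the rule covers.** Planned direct enrollers (Section 12.2): about 100, plus 60 in China, plus 46 in Japan if those are not within the 100.

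- 100 + 60 = 160; 160/400 = 40%.
- 100 + 46 + 60 = 206; 206/400 = 51.5%.

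These counts include children aged 4 and 5, to whom the C-SSRS is not given. The share aged 6 or older and the rate of a Question 4 or 5 Yes are not stated.

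**The case against.** The strongest reply is that this is a slip that the rest of the protocol corrects. Section 8.4.6 itself says the scale is used for screening and follows the visit schedule. Section 5.1 and exclusion 3 place the baseline form before dosing. Criterion 12 is written for all subjects aged 6 or older, whether or not they had a Screening C-SSRS. Table 16-3 applies only to direct enrollers, and its footnote c ends with the since-last-visit version; footnote p of Table 16-1 does the same for the table containing Visit 1. On that reading a site would use the since-last-visit form at Visit 1, and criterion 12 would apply. In any case the scale is still given, its 6-month look-back covers the days since the last TV, and the investigator sees the answer. Mandatory criteria 1 and 8 and optional criterion 1 allow withdrawal.

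Much of this stands. Detection is not lost, general grounds for withdrawal exist, and the intent can be inferred. But the footnotes require an already-enrolled form first, and they do not displace the one sentence that addresses direct enrollers by name. The general grounds depend mainly on investigator judgement and carry no referral instruction. A site that follows 8.4.6 to the letter uses a form to which criterion 12 does not apply. The objection also rightly notes that correcting only 8.4.6 and footnote c would leave footnote p inconsistent at Visit 1.

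**Conclusion.** The concern holds. As written, 8.4.6 gives direct enrollers aged 6 or older a baseline form at an on-treatment visit, and a Question 4 or 5 Yes on that form meets none of the three C-SSRS withdrawal criteria. This assumes the subject had the Screening C-SSRS that Section 5.1 requires; if not, optional criterion 5 would apply.

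The practical gap is small. Because the C-SSRS is also given at every TV, it covers ideation first reported since the final TV (at least 5 days, about a week on the weekly schedule), plus any TV at which a site uses a form other than Since Last Visit. No number of children harmed can be derived from the protocol, and none is claimed. Since the affected rule is a mandatory paediatric suicidality safeguard and the correction is wording only, it should be made.

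**What to change.** In Section 8.4.6, for directly enrolled subjects aged 6 or older, assign the Baseline/Screening version to the Screening Visit, before the first lacosamide dose, and the Since Last Visit version to TV1 and every later visit, including Visit 1. A Question 4 or 5 Yes at Visit 1 then meets mandatory criterion 12.

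Align footnote c of Table 16-3 and footnote p of Table 16-1 with this, so that the already-enrolled form is not requested from a direct enroller who has completed the baseline form. Footnote n of Table 16-2 repeats the same wording and can be tidied at the same time.

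Optionally, extend criterion 12 to a Question 4 or 5 Yes for ideation since the previous assessment, or since the first SP848 dose, on whichever version is used, and leave optional criterion 5 for historical ideation.

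The cost is a sentence in 8.4.6 and the footnotes, plus criterion 12 if the option is taken. No visit or assessment is added, because the C-SSRS is already scheduled at Screening, each TV and Visit 1.
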